1.2 Rationale for Evaluating CX-8998 in Essential Tremor

1.2.1 Cav3 and its Role in Neurological Disorders with Excessive or Abnormal Rhythmicity

Calcium is a ubiquitous intracellular second messenger critical for cellular functions. The elevation of free intracellular Ca^{2+} levels triggers various responses including the activation of Ca^{2+} dependent enzymes, the secretion of neurotransmitters, and muscle contraction. Multiple calcium ion channels regulate calcium influx in response to membrane depolarization, voltage changes, or

substrate, which include the pore-forming alpha₁ subunit Cav3 channel (Catterall, 2005; Adams & Snutch, 2007).

The T-type calcium channel, Cav3, its three (3) isoforms (3.1, 3.2 and 3.3), and their genes *CACNA1G*, *CACNA1H*, and *CACNA1I* were discovered and cloned in the early 1990s, where their function as low-threshold, voltage-gated calcium channel was elucidated (Cribbs et al., 1998). T-type ("T" is for transient) calcium channels are low voltage-activated (LVA) channels predominantly found in neurons. As stated previously, a unique and discriminating property of T-type channels (Cav3) is their ability to activate upon small depolarization of the membrane, contributing to the setting of the resting membrane potential and allowing a surge of calcium entry into excitable cells at the beginning of an action potential. In pathologic states, Cav3 is either upregulated or found to have increased activity, becoming a selective target for specific neurologic diseases (Tai et al., 2011; Park et al., 2010; Bourinet et al., 2005).

Cav3's isoforms are expressed throughout the central nervous system (CNS) and the peripheral nervous system (PNS), including the thalamocortical pathway¹ (Ertel et al., 2000). Deep cerebellar nuclei (DCN), Substantia nigra (SNC), Globus pallidus externa (Gpe), globus pallidus interna (Gpi), subthalamic nucleus (STN), have been noted to have oscillations in healthy hosts and excessive rhythmicity in animals and humans with pathologic conditions of the nervous system. It has been discovered that Cav3 is a mediator of subthreshold oscillations and excessive rhythmicity in pathophysiologic states found in tremor, neuropathic pain, epilepsy and Parkinson's disease (Handforth et al., 2005; Llinás et al., 1999; Llinás, 2003; Park et al., 2013).

The inferior olive (IO) appears to function as a tremor generator and animal models suggest the IO functions as an intrinsic pacemaker (Long et al., 2002). Essential tremor may result from excessive rhythmic synchronous firing of populations of neurons in the IO, which affects the function of the cerebellum (Elble et al., 1996). Cav3 is highly expressed in the IO and the cerebellum. Cav3.1 is the predominate Cav3 isoform expressed in the inferior olive (IO). Within the cerebellar system it is also found on Purkinje cell bodies, DCN, stellate, basket, dendrites and Golgi cells (Molineux et al., 2006). In these locations, Cav3 functions as a tremor generator and ongoing rhythm pacemaker (Park et al., 2010). Park et al. reported that tremor-related oscillations in the olivocerebellar pathways are a neural signature for essential tremor and that Cav3.1 plays a critical role in the onset of tremor-related rhythms (Park et al., 2010).

Harmaline, a plant alkaloid that acts on the cerebellum and IO, induces tremor in animals. Harmaline-induced tremor in animals, like ET, involves the cerebellum. Lesions of the IO reduce harmaline tremors in rats (Simantov et al., 1976). Harmaline tremor is similar to clinical ET in a number of respects, including cerebellar hypermetabolism and a positive response to all known anti-ET agents, including alcohol, primidone, propranolol, gabapentin, zonisamide, and benzodiazepines.

1.2.2 Cav3 Antagonists in Animal Studies

Multiple Cav3-active compounds have been successfully evaluated for their impact on tremor in animal studies. Handforth et al. tested whether both clinically available and experimental

[figure not shown]
¹ Cav3.1 is the most common isoform in the thalamocortical pathway

compounds that antagonize T-type calcium channel currents suppress tremor in two mouse models: harmaline-induced tremor and the GABA(A) receptor α 1 subunit-null model. Mice were administered ethosuximide, zonisamide, the neuroactive steroid ECN, the 3,4-dihydroquinazoline derivative KYS05064, the mibepradil derivative NNC 55-0396, or vehicle. Tremor was measured using digitized spectral motion power analysis. In non-sedating doses, each compound reduced tremor in the harmaline-induced model by at least 50% (range of maximal suppression: 53-81%), and in the GABA(A) α 1-null model by at least 70% (range 70%-93%) (Handforth et al., 2010). Quesada et al. evaluated both mibepradil and NNC-55-0396 in the GABA_{A1} null model and harmaline animal models of tremor and observed reductions in tremor (Quesada et al., 2011).

Tremor suppression by alcohol has been remarked on since the 19th century. Suppression of harmaline tremor by ethanol has been well replicated (Martin et al., 2005; Rappaport et al., 1984). Isomers of octanol (a fatty alcohol) suppress harmaline tremor in rodents (Martin & Handforth, 2006; Sinton et al., 1989); subsequently 1-octanol was found to reduce tremor in ET (Shill et al., 2004). Gamma-hydroxybutyrate also suppresses harmaline tremor and ET tremor (Frucht et al., 2005; Paterson et al., 2009). 1-octanol functions as a Cav3 antagonist (Sinton et al. 1989).

Finally, CX-8998's analogue TTA-P2 has been evaluated in the harmaline model of tremor and demonstrated significant improvement (Figure 1). Rats were placed in one of four conditions, vehicle, versus TTA-P2 1, 3 or 10 mg/kg. TTA-P2 normalized both physiologic tremor prior to harmaline administration and harmaline-induced tremor in a dose-dependent response (Shipe et al., 2008).

Figure 1: TTA-P2 Normalization of Harmaline Tremor in Rats

Rats assigned to vehicle or one of three ascending doses of TTA-P2 demonstrated a dose-dependent response to harmaline-induced tremor following *per os* administration. Prior to administration of harmaline, rats also demonstrated dose-dependent response to a reduction in physiologic tremor (Shipe et al., 2008).

1.2.3 Cav3 as a Target for Treatment of Essential Tremor: Clinical Experience

A number of T-type calcium channel-active compounds have been developed to treat various neurologic diseases which may share a common pathophysiology.

Multiple studies of zonisamide have shown effectiveness in the treatment of tremor as measured by accelerometry and tremor rating scales, however all were limited by poor tolerability and/or excessive premature discontinuations from treatment (Handforth et al., 2009; Zesiewicz et al., 2009; Morita et al., 2005; Bermejo-Pareja et al., 2008; Ondo, 2007; Miwa, 2008). The same finding of effectiveness limited by poor tolerability was also reported for topiramate, a weak Ca_v3 inhibitor (Chang et al., 2015). So, while Ca_v3 is a biologically-validated target for development of ET therapeutics, the search for a safe and effective compound has, to date, been unsuccessful.

[figure not shown]
In summary, the evidence that tremor arises from dysfunction in the inferior-olive – cerebellum network, that excessive rhythmicity may be observed in the thalamocortical network, and that both share mediation via the Ca_v3 calcium channel, whose increased activity is a common pathophysiology, supports the animal and human evaluation results of Ca_v3 antagonists for tremor.

1.3 Non-Clinical Pharmacology

Please refer to the current edition of the Investigator Brochure for a full discussion of prior non-clinical evaluations of CX-8998. CX-8998 is the new name applied to the Merck & Co., Inc. pharmaceutical product known as MK-8998. The name CX-8998 is used here in reference to all prior non-clinical studies conducted by Merck & Co., Inc. CX-8998 was previously investigated for the treatment of insomnia and schizophrenia.

CX-8998, as the HCl salt, is a potent, selective, and state dependent small molecule blocker of T-type calcium channels. The structure of CX-8998 is displayed in Figure 2.

Figure 2: Chemical Structure of CX-8998

[figure not shown]
In vivo pharmacology studies of CX-8998 in rodent and non-human primate sleep architecture have demonstrated dose-dependent increases in slow wave sleep early in the sleep period, followed by a significant increase of rapid eye movement (REM) late in the sleep period. There was also a significant suppression in REM early in the sleep period.

CX-8998 at doses of 1 mg/kg, 3 mg/kg and 10 mg/kg was also shown to dose-dependently inhibit both seizure duration and frequency in a single-dose rat model of absence epilepsy. Additional T-type antagonists from at least five structurally diverse series have shown similar efficacy in this model.

1.3.1 Safety Pharmacology Studies

[figure not shown]
1.4 CX-8998 Clinical Experience

Term	Percentage
GDP	98
Inflation	98
Interest rates	98
Central bank	98
Monetary policy	98
Quantitative easing	98
Inflation targeting	70
Interest rate hike	98
Interest rate cut	98
Inflationary spiral	50

1.4.1 Clinical Pharmacokinetics

Pharmacokinetic data are available from single and multiple dose healthy subject studies (PN001, PN002 and PN005).

1.4.2 Clinical Pharmacodynamics

[REDACTED]

In the current study for essential tremor, a subset of subjects will undergo digital biomarker evaluation to obtain additional pharmacodynamic data pertaining to CX-8998.

1.4.3 Clinical Safety

[figure not shown]
[REDACTED]

1.5 Rationale for Selected Dose

In study PN004, 8 mg twice daily for an average of 4 weeks duration (range 2-29 days) was investigated in adults with acute psychosis (N=86: 49 males and 37 female, 21-55 years old, mean age 37.4 years), and was found to be well-tolerated.

A large black rectangular redaction box covers the bottom half of the page. At the top, there are several smaller black horizontal bars of varying lengths, likely representing redacted text lines.

1. **What is the name of the organization?** [REDACTED]
2. **What is the name of the organization's CEO?** [REDACTED]
3. **What is the name of the organization's CFO?** [REDACTED]
4. **What is the name of the organization's COO?** [REDACTED]
5. **What is the name of the organization's CTO?** [REDACTED]
6. **What is the name of the organization's CIO?** [REDACTED]
7. **What is the name of the organization's CMO?** [REDACTED]
8. **What is the name of the organization's CDO?** [REDACTED]
9. **What is the name of the organization's CDO?** [REDACTED]
10. **What is the name of the organization's CDO?** [REDACTED]

2 STUDY OBJECTIVES

2.1 Primary Objective

To assess the efficacy of CX-8998, in doses up to 10 mg BID in reducing the severity of essential tremor

2.2 Secondary Objectives

1. To assess changes in tremor-affected activities of daily living.
2. To objectively quantify changes in essential tremor severity using accelerometry
3. To assess the safety and tolerability of CX-8998 in doses up to 20 mg per day (10 mg BID)
4. To measure the concentration of CX-8998 and its two primary metabolites (M01 and M02) in plasma

2.3 Exploratory Objectives

1. To assess changes in quality of life in subjects with ET
2. To assess study drug effects on digital biomarker patterns associated with ET (in a subset of subjects).
3. To use the plasma concentrations of CX-8998 and its 2 primary metabolites in population pharmacokinetic/pharmacodynamic (PK/PD) analyses to evaluate exposure-response and exposure-safety relationships

3 STUDY DESIGN AND ENDPOINTS

3.1 Study Type

[figure not shown]
This is a Phase 2, multicenter, double-blind, placebo-controlled, parallel-group study consisting of a screening period of up to 4 weeks (with the exception of subjects on primidone at baseline who will be allowed 6 weeks of screening to allow for safe discontinuation), a 4-week, randomized, double-blind dose-titration treatment period, and a 1-week safety follow-up period following the last dose of study medication.

Subjects will be randomized to one of two treatment groups. Group A will receive titrating doses of CX-8998 up to 10 mg BID and Group B will receive placebo. Subject randomization will be stratified by presence or absence of a single concomitant anti-tremor medication and by site-type (substudy vs. non-substudy).

3.2 Schematic of Study Design

The study design schematic is shown in [Figure 5](#).

Figure 5: Schematic of Study Design

3.3 Endpoints

3.3.1 Primary Endpoint

The change from Baseline to Day 28 on the TETRAS Performance subscale, as scored by the central rater

3.3.2 Secondary Endpoints

1. Change from Baseline to Day 28 on the TETRAS Activity of Daily Living subscale
2. Change from Baseline to Day 28 in accelerometry score, as measured by Kinesia ONE
3. Safety and tolerability endpoints:
 - a. adverse events,
 - b. changes from baseline in QTcF and other ECG parameters,
 - c. clinical safety laboratory assessments (clinical chemistry, hematology, and urinalysis),
 - d. C-SSRS
 - e. Epworth Sleepiness Scale (ESS),
 - f. vital signs,
 - g. number (%) of subjects who did not complete the study,
 - h. number (%) of subjects who did not complete the study due to adverse events.

3.3.3 Exploratory Endpoints

1. Change from Baseline on the Total TETRAS score to Day 15 and Day 28, as scored by the central rater.
2. Change from Baseline to Day 15 on the TETRAS Performance subscale, as scored by the central rater.
3. Change from Baseline to Day 15 in accelerometry score as measured by Kinesia ONE
4. Change from Baseline to Day 15 and Day 28 in Kinesia ONE amplitude measures
5. Treatment success at the end of therapy as measured by Patient Global Impression of Change (PGIC)
6. Treatment success at the end of therapy as measured by Clinical Global Impression of Improvement (CGI-I)
7. Treatment success at the end of therapy as measured by Goal Attainment Scaling (GAS)

8. Change from Baseline in Quality of Life in Essential Tremor Questionnaire (QUEST)
9. Digital biomarkers will be explored in tremor populations of up to 50 subjects using a battery of optional clinical outcomes and digital biomarkers (details will be provided in relevant substudy addendums).

4 STUDY DRUG

4.1 Supply and Storage

CX-8998 will be supplied as 2 mg capsules. Placebo capsules will be matched for CX-8998 capsules and will be indistinguishable from CX-8998 capsules. All manufacturing and packaging activities will be performed according to cGMP guidelines.

Study drug supplies will be stored securely in a temperature-controlled storage area (a locked cupboard or pharmacy with limited access). Only authorized personnel will have access to the study drug. The study site personnel at each site will be responsible for correct storage and handling of the study drug.

Supplies of study drug should be stored below 30° C.

4.2 Packaging and Labeling

[figure not shown]
Study medication will be supplied in 60 cc white HDPE bottles with 33 mm polypropylene, white, child-resistant closures. Each subject will receive a kit with two bottles of active drug or placebo capsules. In each kit, one bottle will contain 80 capsules and the second bottle will contain 150 capsules. The bottles will be appropriately labeled. The affixed label will have spaces for entering the subject number, subject initials, and date dispensed. At the time of dispensing, the subject number, subject initials, and date dispensed are entered onto the appropriate lines on the label.

The label on the product label will contain the following information in the English language:

- Protocol number: CX-8998-CLN2-001
- Expiration date
- Lot number
- Storage conditions
- The sentence, "Caution: New Drug – Limited by Federal Law to Investigational Use"
- Name and address of the sponsor

4.3 Administration

CX-8998 (or placebo) will be administered as 4 mg (2 capsules) twice daily (8 mg/d) in the first week; increasing to 8 mg (4 capsules) BID (16 mg/d) in week 2, to a target of 10 mg (5 capsules) BID (20 mg/d) in weeks 3 and 4.

Treatment compliance will be assessed based on return of unused drug.

Subjects experiencing specified adverse events will have their dose adjusted. See [Section 4.5](#) for details on dose adjustments.

4.3.1 Stopping Rules

Study drug dosing for an individual subject will be permanently discontinued for intolerable AEs that do not resolve to Grade 1 or Baseline within 48 hours of suspension of dosing, and for all Grade 4 AEs. Other reasons for treatment termination are provided in [Section 6.4](#).

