4.5 Dose Adjustments / Toxicity Management

Adverse events will be graded for intensity by the investigator (see [Section 10.2.2.2](#)).

Dosing will be discontinued for all Grade 4 AEs.

In all subjects with intolerable AEs (as defined in [Section 10.2.1](#)) that are considered related to study drug, treatment should be suspended for up to 48 hours or until the AE resolves to a tolerable level of severity, whichever is earlier. Dosing may then be resumed at a previously tolerated lower dose (or 2 mg BID in the case of 4 mg BID). Only a single dose-step reduction (e.g. 10 mg BID to 8 mg BID, 8 mg BID to 4 mg BID, or 4 mg BID to 2 mg BID) is permitted. Re-up-titration is NOT permitted. Dosing should be discontinued if there is recurrence of intolerable AEs after dose reduction. Subjects on the 2 mg BID dose with intolerable AEs will be discontinued from treatment. Table 2 details dose reductions by dose level.

All subjects who discontinue treatment due to AEs will be followed for AE outcome. All AEs should be followed for resolution or for 30 days from the last dose of study drug, whichever is shorter.

Table 2: Study Drug Dose Reduction for Intolerable AEs

Dose and Schedule of Study Drug	Dose Reduction
2 mg BID	Remove from treatment ¹
4 mg BID	2 mg BID
8 mg BID	4 mg BID
10 mg BID	8 mg BID

1 – Subjects who are removed from treatment for AE(s) should be followed for resolution of the AE(s) and should complete all assessments scheduled for the EOS/FU Visit as well as all assessments that they are capable of completing on the Visit day if the decision to remove from treatment is made on a Visit day. Likewise, if the investigator plans to temporarily interrupt dosing because of an AE and the decision is made on a visit day, then the subject should complete all scheduled assessments that they are capable of completing on the visit day they appear.

The study safety representative should be notified of all dose reductions as soon as is feasible.

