10.2 Adverse Events

10.2.1 Definitions

Adverse Event

An Adverse Event (AE) is any unfavorable or unintended sign (including an abnormal laboratory finding), symptom, or disease temporally associated with the use of a medical

treatment or procedure that may or may not be considered related to the medical treatment or procedure.

Laboratory Abnormality

A laboratory abnormality is any clinically significant laboratory abnormality suggesting a disease or organ toxicity and which is of a severity requiring active management (i.e., changes of dose, discontinuation of drug, more frequent follow-up, medical treatment or a diagnostic investigation). Laboratory abnormalities are also considered AEs.

Treatment-emergent Adverse Events

Treatment-emergent adverse events (TEAEs) are all AEs occurring during the treatment period or a pretreatment event that worsens in intensity during the treatment period.

Treatment Period

The treatment period is the period during which a subject receives study drug (i.e., first dose through 30 days after last dose).

Intolerable Adverse Event

An intolerable AE is one that is considered by the investigator to be related to study drug ([Section 10.2.2.3](#)) AND is either a Grade 3 (severe) or 4 (life threatening) event ([Section 10.2.2.2](#)) OR is a Grade 1 or 2 event that prompts the subject to express a desire to discontinue dosing. Dose adjustments for intolerable AEs are described in [Section 4.5](#).)

Serious Adverse Event

A serious adverse event (SAE) is any adverse event that results in death, is life-threatening, requires in-patient hospitalization or prolongation of existing hospitalization, results in persistent or significant disability/incapacity, is a congenital anomaly/birth defect observed in any offspring of the subject conceived during treatment with the study drug or is an important medical event. See [Section 10.3](#) for more details on SAEs.

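### For a defined subset of intolerable adverse events, section 4.3.1 requires a permanent stop where section 4.5 permits resumption at a lower dose, and nothing says which section governs

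*Protocol*

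**What the plan says.** All references are to the latest protocol version, the one that plans about 106 subjects.

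- **Section 4.3.1 (Stopping Rules)** is mandatory. Dosing will be "permanently discontinued for intolerable AEs that do not resolve to Grade 1 or Baseline within 48 hours of suspension of dosing". It also stops every Grade 4 event, and it sends the reader to section 6.4 for other reasons to end treatment.
- **Section 4.5 (Dose Adjustments / Toxicity Management)** covers intolerable events considered related to study drug. It says "treatment should be suspended for up to 48 hours or until the AE resolves to a tolerable level of severity, whichever is earlier", followed by "Dosing may then be resumed at a previously tolerated lower dose" (2 mg BID for a subject on 4 mg BID). Only one step down is allowed. The section adds "Dosing will be discontinued for all Grade 4 AEs" and "Dosing should be discontinued if there is recurrence of intolerable AEs after dose reduction", and it removes from treatment any subject with an intolerable event on 2 mg BID.
- **Section 10.2.1 (Definitions)** requires an intolerable event to be related to study drug. It then gives two routes: "AND is either a Grade 3 (severe) or 4 (life threatening) event" and "OR is a Grade 1 or 2 event that prompts the subject to express a desire to discontinue dosing".

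**The concern.** Sections 4.3.1 and 4.5 both decide what happens to a subject whose dosing has been suspended for an intolerable event, and both use 48 hours. They do not use the same recovery test. Section 4.3.1 asks for a return to Grade 1 or Baseline. Section 4.5 asks only that the event be tolerable, names no grade, and lets the suspension lapse at 48 hours in any case.

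The definition in 10.2.1 keeps these tests apart. Below Grade 3, an event is intolerable only if it makes the subject want to stop, so a Grade 2 event that the subject accepts is tolerable. It has still not reached Grade 1.

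What is at stake is a safety instruction: whether a subject stays on an investigational drug after a severe or unwelcome related event. The same instruction affects who is still on treatment at Day 28, when the primary endpoint is measured. Subjects who stop early are not replaced (6.4.2).

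**Working it through.** No sample size, power or event count enters this point, and the plan gives no figure to reproduce. The check sets the two sections side by side and works through the possible courses of an event.

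**Step 1. Scope.** Take a related intolerable event in a subject on 4, 8 or 10 mg BID with no earlier dose reduction. Subjects on 2 mg BID and subjects whose intolerable event recurs after a reduction are left out, because section 4.5 itself stops them.

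**Step 2. Apply both sections to each course.** Grades in (c) to (e) are taken to be above the subject's Baseline level.

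| Course of the event | Section 4.3.1 | Section 4.5 | Result |
|---|---|---|---|
| (a) Grade 4 | stop | stop | agree |
| (b) Grade 2 or 3, reaches Grade 1 or Baseline within 48 h | not triggered | lower dose permitted | agree |
| (c) Grade 3, falls to a tolerable Grade 2 within 48 h and no lower | permanent stop | lower dose permitted | conflict |
| (d) Grade 2, becomes tolerable to the subject but is still Grade 2 at 48 h | permanent stop | lower dose permitted | conflict |
| (e) Grade 2 or 3, still intolerable at 48 h | permanent stop | lower dose permitted on the literal text, because the suspension runs for at most 48 h | conflict on the literal text |
| (f) Grade 1 that makes the subject want to stop | not triggered | suspend, then lower dose permitted | agree |

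Three of the six courses conflict. Courses (c) and (d) follow directly from the different recovery tests. Course (e) depends on reading section 4.5 word for word.

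**Step 3. Timing.** In (c) and (d), section 4.5 ends the suspension as soon as the event is tolerable. Suppose a Grade 3 event becomes a tolerable Grade 2 at 24 hours (an illustrative time). Section 4.5 then permits a restart at the lower dose. If the event is still Grade 2 at 48 hours, section 4.3.1 requires a permanent stop for a subject already restarted under section 4.5. Section 4.3.1 counts from the suspension and makes no exception for a subject who has restarted.

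**Step 4. Look for a tie-breaker.**

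- Sections 4.3.1 and 4.5 do not cite each other.
- Section 4.3.1 points to 6.4. Section 6.4 lists unacceptable toxicity as a reason to stop and refers to 4.5 for it, not to 4.3.1.
- Section 10.4 item 5 cites only 4.5 for both dose modification and stopping rules, although 4.3.1 is the section that carries the title Stopping Rules.
- The synopsis (Study Design) and section 10.4 item 3 allow a dose reduction for an intolerable event without the Grade 1 or Baseline condition.

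None of these ranks the two sections.

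**The case against.** The strongest defence is that the two sections are not opposing commands. Section 4.5 only permits resumption, while 4.3.1 requires a stop, so a site that treats 4.3.1 as a limit on 4.5 complies with both. This has force: nobody is ever obliged by section 4.5 to restart. But the protocol does not state that limit, and the cross-references point to 4.5 rather than to 4.3.1. The defence is weakest on timing, because section 4.5 allows a restart before the moment at which 4.3.1 can be judged.

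It can also be said that the investigator may stop treatment in the subject's interest under either section (6.4), and that the study safety representative is told of every dose reduction (4.5). Both are true and soften the practical effect. Neither supplies the missing rule, and different handling across sites is plausible but not shown.

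Three stronger readings may tempt a reader, and the documents do not support them.

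- **That every intolerable event still at Grade 2 or above at 48 hours is affected.** Both sections stop Grade 4 events. Section 4.5 itself stops subjects on 2 mg BID and recurrences after a reduction. An event back at a Baseline level of Grade 2 or higher satisfies 4.3.1.
- **That an intolerable Grade 1 event is left without a rule.** Section 4.3.1 does not reach it, but 4.5 does: suspend, resume lower, stop on recurrence. That is no contradiction.
- **That the conflict uses up the sample-size allowance for dropouts.** The protocol gives no rate for these events. Stopping treatment is also not removal from analysis, because the ITT population used for efficacy includes all randomized subjects, analysed as randomized (11.4).

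**Conclusion.** The conflict is real and limited. It applies to a related intolerable event below Grade 4, in a subject on 4, 8 or 10 mg BID with no earlier dose reduction, that is still above both Grade 1 and Baseline 48 hours after suspension. For that subject section 4.3.1 requires permanent discontinuation and section 4.5 permits a lower dose, possibly from before the 48-hour point.

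The number of subjects affected cannot be computed from the protocol, and no consequence for power is claimed. The conclusion rests on the wording of the two sections, on the definition of an intolerable event in 10.2.1, and on the absence of any text that ranks the sections. It needs no assumption about event rates. It takes no position on which clinical rule is right. The point merits correction because an individual stopping rule should give one answer for one subject.

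**What to change.** Reconcile sections 4.3.1 and 4.5 so that one resolution criterion and one consequence at 48 hours apply. State how that criterion bears on a subject who restarts before 48 hours. Bring the synopsis (Study Design), section 6.4 and section 10.4 items 3 and 5 into line, so that every reference leads to the same rule. The clinical team must choose the criterion and the consequence.

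The cost is amended protocol wording and a memo to sites. No new data, visits or staff are needed.
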